1. BACKGROUND AND RATIONALE

The Problem with Self Harm

Self-harm behaviour is an act of self-injury regardless of intent (NICE, CG133). Prevalence is high with an estimated 20% of young people (YP) under 25 self-harming (Gillies et al. 2018).

Methods of self-harm can be broadly divided into self-injury (e.g., cutting, bruising, burning, selfbattery) and self-poisoning (most frequently overdose of prescribed or over-the-counter medication). Method switching is common (Lilley et al., 2008) and co-occurrence of multiple methods is used as an index of severity (DSM-5, 2013). Individuals vary in the motives that drive and trigger self-harm. A recent study reported that getting "relief from a terrible state of mind" was the most common reason for self-harm in both boys and girls aged 14-16 (Rasmussen et al., 2016). Motives also change from episode to episode: a study of over 30,000 adolescents in seven countries described that over 80% of those who had harmed themselves in the previous month reported more than one reason for self-harm, including wanting to get relief from a terrible state of mind, wanting to die and wanting to punish oneself (Scoliers et al., 2009).

While most self-harm cases particularly in adolescents represent a form of transient distress, selfharm is more prevalent in those who suffer from a mental disorder. Symptoms of depression, anxiety, as well substance abuse are risk factors for self-harm behaviour and in particular for its repetition. For example, those who start self-harming as young adults are more likely to have presented with symptoms of depression and anxiety since adolescence (Uh et al. 2021). Adolescents who self-harm also have poorer educational and social outcomes (Mars et al. 2014). Self-harm is the strongest risk factor for suicide (Wilkinson et al. 2011): with those who self-harm estimated to be 17 times more likely to die by suicide than those who do not (Morgan et al. 2017).

In summary, self-harm in YP is a major social and healthcare problem. It represents significant morbidity, is often repeated, and has links to suicide, with substantial healthcare costs for the community. Effective early intervention would therefore be of great benefit.

Current Interventions

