2. CASE SERIES EVALUATION

2.1 OVERVIEW OF METHODOLGY

We will run a case series study that investigates the IMAGINATOR intervention comprising of delivery of Functional Imagery Training (FIT) for self-harm supported by a new co-designed smartphone app to YP aged 12-25 who experience current repeated self-harming behaviour and have been referred to WLT teams, which includes the adult community mental health services (Mental Health Integrated Network Teams; MINT) and the Community Child and Adolescent Mental Health Services (CCAMHS). For the purpose of this study, self-harm is defined as per NICE

guidelines (NICE, 2012): "an act of self-poisoning or self-injury, irrespective of the apparent purpose of the act".

A case series is a descriptive study that follows a group of patients who have a similar diagnosis or who are undergoing the same procedure over a certain period of time and is the most appropriate design for reporting on a novel therapeutic intervention with a new population. The IMAGINATOR intervention has been tested with 16-25 year olds using a proof of concept trial ([name] et al., 2020) but as the current study proposes to also include younger participants (12-17 year olds) and a newly developed version of the IMAGINATOR app, a case series is the optimal design to assess the feasibility and acceptability of the new IMAGINATOR intervention following further protocol/materials development and with a different population.

The IMAGINATOR intervention provides three sessions of FIT + Standard Care (SC), followed by phone support sessions and smartphone app-based support, based on cognitive behavioural and motivational interviewing principles and in line with NICE guidelines for long-term management of self-harm behaviour. FIT is intended as a brief and focused transdiagnostic intervention that can be added to any other pharmacological or non-concurrent psychological therapy. To improve YP's access to and engagement with the intervention, we will deliver FIT face-to-face and encourage participants to support their therapy by using the new IMAGINATOR smartphone app.

The study will be based in the West London NHS Trust.

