2.4 ENDPOINTS

Primary Endpoints

Feasibility: An indication of feasibility assessed by calculating treatment adherence indicators such as the average number of therapy sessions completed by participants, the percentage of participants completing different components of the intervention (face-to-face sessions, phone calls), and attrition (the percentage who complete post-intervention assessment).

Acceptability: An indication of acceptability assessed by calculating scores on Credibility/Expectancy Scales, the Client Satisfaction Questionnaire, User Experience Questionnaire and other bespoke acceptability measures identified by the YPAG, and by analysing qualitative data obtained through the Experience of Service questionnaire and semi-structured feedback interviews.

Safety: Safety of the intervention determined by reviewing *adverse events* recorded at each assessment and therapy session/phone call contact.

Secondary Endpoints

Potential effectiveness of the IMAGINATOR intervention:

Change assessed from pre-FIT intervention to post-FIT intervention, and at 6 months follow up in the following outcomes:

- a) Average frequency of self-harm, and average severity of self-harm scores over the past 3 months
- b) Average scores on questionnaires of clinical, functional and process outcomes (see Assessments)
- c) Proportion of YP needing further treatment in CCAMHS/MINT/other WLT services vs can be closed to CCAMHS/MINT/other WLT services
- d) Emergency department visits.

Potential mechanisms:

Change assessed from pre-FIT intervention to post-FIT intervention, and at 6 months follow up in the following outcomes:

- a) Average scores on characteristics of mental imagery associated with self-harm when present (e.g. vividness, compellingness)
- b) Average scores of the urge to self-harm
- c) Average scores on emotion regulation ability measures.

Potential effectiveness of the *IMAGINATOR* app:

a) Correlations between endpoint scores (listed above) and the following measures of *IMAGINATOR* app use: number of app sessions/logins and total duration of app use, number of activity cycles completed, number of personalised media uploaded, number of completed guided imagery sessions, total duration of guided imagery completed and use of any other key functionalities at 6 months follow up.

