2.8 ASSESSMENTS AND QUESTIONNAIRES

1) The following measures are collected during the **Baseline Screening Visit** and again during the **Outcome Assessments (post intervention and at 6 months follow-up):**

Self-harm measures

Administered by researcher:

- a) Self-harm frequency over the past 3 months: Using the timeline follow-back technique (TLFB, Sobell & Sobell, 2008). This is an interview method conducted by the researcher who reconstructs together with the participant the number of self-harm behaviours using calendar cues. It has been successfully used in previous self-harm research including our proof-of-concept study ([name] et al., 2020; Maschauer et al., in preparation).
- b) Self-harm severity over the past 3 months: A combined measure of a Visual Analogue Scale, severity criteria used in the NSSI disorder in the Diagnostic and Statistical Manual of Mental Disorder Fifth Edition (DSM-V, 39) and the number of different self-harm methods used (also termed self-harm versatility), elicited via these open questions: "In the last three months, how severe was the worst injury that you inflicted to yourself? Can you list all the ways that you have used to harm yourself in the last three months?" This method was advised by the YPAG to avoid scales listing numerous self-harm methods which could be triggering/enabling.
- c) **Mental imagery related to self-harm:** Using the *Self-Harm Imagery Interview* adapted from (Hales et al., 2011): This interview is about mental images that deal with self-harm or occur with self-harm. It asks participants to think about one of these and explores their thoughts and emotions in relation to the image.
- d) Suicidal thoughts and behaviour: Using the *Columbia-Suicide Severity Rating Scale* (C-SSRS) (Posner et al., 2011) is widely used interview for suicide risk assessment and

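### The only graded severity question asks about the worst injury, so the severity of self-poisoning, which the study definition includes, is not explicitly elicited

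*Combined protocol and SAP*

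**What the plan says.** Section 2.1 fixes the definition used in the study: "an act of self-poisoning or self-injury, irrespective of the apparent purpose of the act". Section 1 divides methods into self-injury and "self-poisoning (most frequently overdose of prescribed or over-the-counter medication", and adds that "Method switching is common". Nothing in the eligibility criteria (section 2.6) excludes people who self-poison.

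Section 2.8(b) describes self-harm severity as a combined measure with three components: a visual analogue scale (VAS), severity criteria from DSM-5 non-suicidal self-injury disorder, and the number of methods used. It is elicited by two open questions put by the researcher. The first is "In the last three months, how severe was the worst injury that you inflicted to yourself". The second is "Can you list all the ways that you have used to harm yourself in the last three months". The open format was chosen on the advice of the Young Persons Advisory Group (YPAG), which wanted to avoid long lists of methods. Section 2.7 (Collection of Baseline Measures) lists the two-item severity questionnaire among the measures designed specially for this study.

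The result feeds secondary endpoint (a) in section 2.4: "Average frequency of self-harm, and average severity of self-harm scores over the past 3 months".

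**The concern.** The definition has two branches and the graded question names one of them. Someone whose self-harm in the past three months was an overdose may reasonably answer that there was no injury, or may rate a lesser injury instead. The overdose would then appear as an entry in the list of methods, with no rating of how serious it was.

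This matters most for change over time. If a participant moves from injury to overdose between visits, the rating can fall although self-harm continues, and secondary objective 1(a) would record that as improvement. With about 15 completers summarised by means, percentage change and Cohen's d (section 2.9), one or two such participants would be visible in the result. Section 1 also foresees a later randomised trial, to which the measure might be carried forward.

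**Working it through.** **1. The plan's own figure.** Section 2.9 aims for 15 completers and expects 25% attrition: 15 / (1 − 0.25) = 20, which matches the stated enrolment. The plan states no power, alpha or effect size. Only the 15 is used below.

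**2. What each measure captures for self-poisoning.**

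| Measure | Self-poisoning covered? | Severity graded? |
|---|---|---|
| 2.8(b), question 1 (worst injury) | Not on a literal reading | Yes |
| 2.8(b), question 2 (all ways of harming) | Yes, as a method | No, counted only |
| 2.8(a), timeline follow-back | Yes, as an episode | No, counted only |
| 2.8(d), C-SSRS | Presented for suicidal thoughts and behaviour | Yes, 6-point lethality rating |
| 2.7, emergency department attendance | Attended episodes only | No |

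Within the severity measure, no question asks how severe a self-poisoning episode was.

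**3. Direction of change on a literal reading of question 1.**

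- One injury method is replaced by overdose: the method count stays at 1 and the rating falls to none or to a lesser injury. The measure falls.
- Overdose is added to continuing injury: the count rises from 1 to 2 and the injury rating need not change. The measure does not fall.
- The participant treats the overdose as the worst injury: it is rated, and nothing is lost.

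The favourable error therefore needs two conditions: injury stops or lessens, and the overdose is left out of the answer to question 1.

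**4. Size, on assumptions that are not in the documents.** Assume a VAS from 0 to 10. Let the baseline mean, also the switcher's own baseline, be b = 4 to 6, with SD s = 2 to 3. Switchers answer p = 0 to 2 afterwards, and nobody else changes. For k switchers among 15 completers:

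- fall in mean = k(b − p)/15
- percentage fall = 100 × k(b − p)/(15b)
- apparent d = k(b − p)/(15s)

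For k = 1 the smallest fall is (4 − 2)/15 = 0.13 and the largest is (6 − 0)/15 = 0.40. The d values run from 0.13/3 = 0.04 to 0.40/2 = 0.20.

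| Switchers | Fall in mean | Percentage fall | Apparent d |
|---|---|---|---|
| 1 | 0.13 to 0.40 | 3.3 to 6.7 | 0.04 to 0.20 |
| 2 | 0.27 to 0.80 | 6.7 to 13.3 | 0.09 to 0.40 |
| 3 | 0.40 to 1.20 | 10 to 20 | 0.13 to 0.60 |

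These figures concern the VAS rating alone. The effect on the combined score cannot be calculated, because no rule for combining the components is given.

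**The case against.** The strongest reply is that the measure is wider than its first question and the study is wider than the measure. Question 2 brings an overdose into the same combined score. A researcher administers the item and can clarify it. Section 1 also uses injury as an umbrella term: "Self-harm behaviour is an act of self-injury regardless of intent". A participant might therefore rate an overdose as the worst injury. Outside the measure, timeline follow-back would count the episodes and is the other half of the same endpoint. Emergency department attendance is an endpoint of its own, adverse events are recorded at every contact, and a hospitalisation would generally be a serious adverse event (section 3.3). Medians and interquartile ranges are reported as well as means. A participant who moved to overdose would not vanish from the study's records.

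Much of this stands, and it limits the point to one sub-score. It does not remove it. Question 2 and the follow-back record that an overdose happened, not how severe it was. A few overdoses in place of many injuries would also lower the frequency count. The C-SSRS is presented as a measure of suicidal ideation and behaviour, whereas the study definition applies whatever the purpose. Emergency department records miss unattended episodes. Clarification by the researcher helps only if all researchers clarify in the same way, and section 2.8 gives no guidance on this. If some participants count overdose as injury and others do not, their ratings are not comparable.

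**Conclusion.** The mismatch between definition and question is real and worth correcting. The severity of self-poisoning is not explicitly elicited, and a switch from injury to overdose can read as improvement on the severity part of secondary endpoint (a). The size cannot be established: the documents give no VAS range, scoring rule or switching rate. Under the assumptions above, one switcher moves the mean rating by about 0.1 to 0.4 points and three move it by 0.4 to 1.2. The primary endpoints, the sample size and error rates are unaffected.

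A reader might infer three stronger things that the documents do not support:

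- *That overdose severity is never scored.* No scoring rule or interviewer guidance shows this, and the umbrella use of injury in section 1 leaves room for it to be rated.
- *That the score moves the wrong way for anyone who turns to overdose.* It need not fall where injury continues or where the participant rates the overdose. Section 1 gives neither a rate nor a direction for method switching.
- *That the number of methods is counted twice.* Section 1 says of DSM-5 that "co-occurrence of multiple methods is used as an index of severity", and section 2.8(b) lists method count beside DSM-5 criteria. The plan does not say which criteria are scored or how the components combine, so this cannot be determined.

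**What to change.** Reword question 1 in neutral terms that match the definition and name no methods, for example: *Over the past three months, how severe was your most serious episode of self-harm?* Use identical wording at baseline, post-intervention and 6 months. State in the researcher's guidance that self-poisoning counts as an episode. Report the severity rating alongside the number of methods, so that a change in one is not masked by the other; if a combined score is kept, state how it is formed. For anyone already assessed under the existing wording, state how self-poisoning was rated.

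The cost is one study-specific Qualtrics item, a short guidance note, and a line each in sections 2.8 and 2.4. Because the new wording lists no methods, it respects the YPAG's reason for the open format. The small downside is that the item is no longer worded as a worst-injury item.

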2.9 DATA ANALYSIS

Sample Size

We aim to reach N=15 participants who will complete treatment and 6 months follow-up assessments. Based on an expected 25% attrition rate from our previous study ([name] et al., 2020), N=20 participants will be enrolled in the study.

Statistical Analysis

Quantitative data will be summarised into descriptive statistics such as means, medians, inter quartile range, standard deviations for all measures and percentage change and Cohen's *d* for the clinical outcomes repeated at pre- and post-intervention. Qualitative data will be analysed using a co-produced thematic analysis approach based on Braun & Clarke (2006) and Dewa et al. (2021a, 2021b). Data and all appropriate documentation will be stored for a minimum of 10 years after the completion of the study, including the follow-up period.

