To assess risk and adverse events, at the beginning of each session the therapist conducts the Columbia-Suicide Severity Rating Scale (C-SSRS) interview.

Follow-up Phase

Follow up and support sessions: The Follow Up phase involves five support phone calls by the therapist/CWP/CAPT who conducted the FIT. The first phone support takes place one week after the second FIT session (approx. 30 mins duration). This session focuses on refining the functional imagery practice and problem-solving obstacles to training the imagery techniques. Suggestions - aim to incorporate the *IMAGINATOR* app as much as possible if the participant feels this is useful, for example discussing how the different app functionalities can be used, personalised and maximised to support the FIT.

Four further phone support sessions (approx. 15 mins each) are then delivered fortnightly, which focus on further problem-solving, motivational encouragement and discussion of how to maximise the *IMAGINATOR* app use.

To assess risk and adverse events, the therapist will conduct a clinical risk assessment at the beginning of each phone session.

IMAGINATOR app-based support: The IMAGINATOR app was co-designed with YP with lived experience of self-harm (see 2.2. Co-production). It is used by participants as a support to keep practicing and training FIT to achieve their behavioural change goal during the study follow-up IMAGINATOR 2.0

phase. The IMAGINATOR app does not introduce any new element from what has been discussed and developed in the FIT face-to-face sessions and is neither intended to nor designed to be used as a self-standing tool. To ensure confidentiality, the IMAGINATOR app makes no reference to self-harm and all push-ups and notifications only refer to 'IMAGINATOR'.

Routine follow-up: The therapist/CWP/CAPT) will follow up routinely with the young person at 16 – 18 weeks.

Outcome Assessments (post intervention and 6 months follow-up)

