measurement of suicidal ideation and behaviour. The *Lifetime/Recent* version will be used at screening to gather recent history of suicidality including suicidal ideation and/or behaviour. The scale measures four constructs: severity of ideation on a 5-point ordinal scale (from 1=wish to be dead, to 5=suicidal intent with plan); intensity of ideation via 5 items (e.g. frequency, duration etc.), each rated on a 5-point ordinal scale; behavior rated on a nominal scale (including actual, aborted, and interrupted attempts, preparatory behavior and non-suicidal self-injurious behavior); and lethality rated on a 6-point ordinal scale. **This measure will additionally be used at the start of each face-to-face FIT session.**

e) Motivation to reduce self-harm: Using the State Motivation for Reducing Self-harm (SM-SH) scale (Parham et al., 2017). This scale measures participants' motivation to control their self-harm using 12 items that measure the strength of their motivational cognitions in the present moment, rated on a 10-point likert scale, from 0 (never) to 10 (constantly).

Self-report:

f) Urge to self-harm: Using the Craving Experience Questionnaire for Self-Harm (CEQ-SH), adapted from CEQ (May et al., 2014) This questionnaire assesses the urge to self-harm and assesses frequency, intensity, salience or dismissability of intrusive thoughts surrounding self-harm. It is rated on a 10 point Likert type scale ranging from not at all (0) to constantly (10).

Clinical and functional measures

Self-report:

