Secondly, all researchers conducting eligibility assessment at the baseline screening visit will be trained and supervised by expert clinicians who will also provide cover at the time of the assessments ('duty clinicians').

The study therapists are qualified CWP/CAPTs or other clinicians (e.g. medical doctor) who are trained to deliver GSH interventions to YP with low mood or anxiety. They are used to discussing upsetting experiences with YP in a way that is collaborative, puts the young person at ease and is perceived as useful and necessary for aiding symptoms resolution by both therapist and patient. Moreover, these clinicians are well equipped to make sure that any distressing session ends by the participant feeling supported and endowed with the necessary coping strategies in place to go safely back to their home environment.

Case management supervision for the therapists/CWPs/CAPTs will be provided through routine weekly individual sessions with their supervisors and group clinical skills supervision will be provided the study therapist.

Therapists/CWPs/CAPTs and researchers will always remain sensitive to signs of participant distress and will terminate the assessment or specific intervention, or the session itself, if the participant becomes distressed and wants to stop. In our experience, it is rarely, if ever necessary

that clinical interviews are interrupted, as participants are aware of what the interviews will entail and are readily able to answer the questions they contain. Researchers will also check the participant's mood state and safety upon completion of the self-report questionnaires during the Baseline Screening and Outcome Assessments Visits.

The *risk (ii) i.e. of disclosing information that is relevant to the participant's safety and health,* such as a mood state that meets criteria for a tier 3 intervention (e.g., psychosis or eating disorder), or the presence of suicidal risk, will be addressed by putting in place the following series of procedures that will ensure the participant is safe and their mental state is taken into account:

- Review confidentiality with young person
- Supportively assess risk (in terms of safeguarding or clinical risk)
- Carry out all possible interventions to reassure, support, reduce active distress to the minimum possible once this has become apparent;

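### The C-SSRS serves partly as a safety measure, but the plan states only group-level summaries for it and no count of participants who worsened, so individual deterioration can sit inside an average improvement

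*Combined protocol and SAP*

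**What the plan says.** **Purpose and timing.** Section 2.8 schedules the C-SSRS at baseline, post-intervention and 6 months, and also at the start of each face-to-face FIT session. For the sessions, section 2.7 says: "To assess risk and adverse events, at the beginning of each session the therapist conducts the Columbia-Suicide Severity Rating Scale (C-SSRS) interview". The phone sessions have a clinical risk assessment, and the C-SSRS is not named there.

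**Scale.** Section 2.8 describes "severity of ideation on a 5-point ordinal scale (from 1=wish to be dead, to 5=suicidal intent with plan". It rates behaviour on a nominal scale.

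**Endpoint.** Section 2.3 lists suicidal thoughts and behaviour as a secondary objective, under potential effects. The matching endpoint in section 2.4 appears to be "Average scores on questionnaires of clinical, functional and process outcomes (see Assessments", under potential effectiveness.

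**Analysis.** Section 2.9 says "Quantitative data will be summarised into descriptive statistics such as means, medians, inter quartile range, standard deviations for all measures and percentage change", and adds Cohen's d for clinical outcomes repeated before and after the intervention.

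**Safety.** The primary safety endpoint in section 2.4 is a review of adverse events recorded at every contact. Section 3.3 defines an adverse event in general terms and does not mention the C-SSRS. Section 3.2 recognises the risk: "or the presence of suicidal risk, will be addressed by putting in place the following series of procedures".

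**The concern.** Safety is one of three primary objectives, and the age range now starts at 12, where the proof-of-concept study started at 16. For a measure used to watch for harm, the natural question is how many participants got worse than they were at entry. A group mean answers a different one. A mean or Cohen's d of an ordinal score lets many small improvements cancel a few large deteriorations, and neither has a meaning for a nominal behaviour category.

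At stake is a report that shows lower average suicidality while saying little about the individuals who moved the other way. Worsening that a therapist or researcher did not judge to be an adverse event would then appear in no planned participant-level summary.

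**Working it through.** **1. The plan's own figure.** Section 2.9 sets the completer target: "We aim to reach N=15 participants who will complete treatment and 6 months follow-up assessments". It allows for 25% attrition and plans to enrol 20. Check: 15 / (1 − 0.25) = 20. This agrees.

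**2. Contacts.** Baseline 1 + FIT sessions 3 + post-intervention 1 + 6 months 1 = 6. The change endpoint in section 2.4 (pre, post, 6 months) covers three of them. Percentage change and Cohen's d are stated for pre to post only.

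**3. Can the stated summaries hide worsening?** The scores below are assumed. The scale is the protocol's 1 to 5 ideation scale, with 15 completers. Thirteen participants go from 3 to 2, and two go from 1 to 5.

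- Mean before: (13×3 + 2×1)/15 = 41/15 = 2.73
- Mean after: (13×2 + 2×5)/15 = 36/15 = 2.40
- Mean change: −5/15 = −0.33; percentage change: −5/41 = −12.2%
- Median: 3 to 2; interquartile range after: 2 to 2
- Variances: 6.93/14 = 0.495 before, 15.6/14 = 1.114 after, so the SD goes from 0.70 to 1.06
- Cohen's d, averaged variance: −0.333/√((0.495 + 1.114)/2) = −0.37
- Cohen's d, SD of change: −0.333/√(43.33/14) = −0.333/1.76 = −0.19
- Participants who rose to level 5: 2/15 = 13.3%, Clopper–Pearson 95% CI 1.7% to 40.5%

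Mean, median, interquartile range, percentage change and both forms of d all read as improvement. Only the SD hints otherwise, and it shows neither direction nor how many.

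**4. Does this depend on one example?** Take 12 participants from 3 to 1 and 3 from 2 to 5. The mean falls from 2.8 to 1.8 (−36%), and d is −0.83 (averaged variance) or −0.48 (SD of change). Yet 3/15 (20%, CI 4.3% to 48.1%) reach the top level. In general, if k participants rise by u and the rest fall by v, the mean still improves while k < 15v/(u + v). For u = 2, v = 1, k can be up to 4. For u = v = 1, k can be up to 7.

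**5. What a count would deliver.** With no worsening among 20 assessed, the exact upper 95% limit is 1 − 0.025^(1/20) = 16.8%. With 15 assessed it is 21.8%. One case in 20 gives 0.1% to 24.9%.

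**6. Why the count should be made at each time point.** Suppose nothing changes, the six readings are exchangeable, and there are no ties. The highest of five later readings then exceeds the baseline reading with probability 5/6 = 83%, against 1/2 for a single later reading. Ties lower both. A simulation on a rounded 0 to 5 scale (assumed SD 1.3, within-person correlation 0.5 to 0.85) gave 47% to 68% for the worst-of-five comparison. A worst-value count would therefore call many participants worse through fluctuation alone.

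**The case against.** The strongest reply is that the C-SSRS already feeds the safety endpoint. Section 2.7 has it done in sessions to assess adverse events, section 2.4 has adverse events recorded at every contact, and section 3.3 has all of them reported. Section 3.3 also treats as serious an event that may jeopardise the participant. Someone who reached intent with a plan would probably be captured there, and section 3.2 requires escalation. This stands. A reader might infer that worsening suicidality is left out of the primary safety result, and the documents do not support that. What remains is that the text supplied does not say which C-SSRS change is to be recorded as an adverse event. Some text beside section 3.3 is not in the copy available, so this is a statement about the text supplied.

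A reader might also infer that the C-SSRS will be analysed only as an average. That too goes beyond the text. The list in section 2.9 is given as examples and includes spread. Endpoint (b) in section 2.4 speaks of questionnaires and does not name the C-SSRS, which is an interview listed under self-harm measures. Even so, an open list is not a pre-specified participant-level summary.

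Finally, this is a descriptive case series of 20, so one more table is a reporting refinement. That is fair, and it limits how much weight the point carries.

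**Conclusion.** The concern holds as a gap in planned reporting. The summaries stated for the C-SSRS are group-level, unsuited to its ordinal and nominal parts, and able to hide marked worsening in a few of about 15 completers: 2 or 3 of 15 in the worked examples, and up to 4 of 15 when those who worsen rise two points and the rest fall one. The scores are assumed. They show that masking is possible at this size, not that it is likely.

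The documents do not show that serious suicidality escapes the safety endpoint. The exposure is mainly to milder worsening, whose recording rests on the judgement of therapists in sessions and researchers at assessments. No sample-size figure is affected. Because the point bears on a primary objective and uses measures already scheduled, it is a worthwhile and cheap improvement.

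**What to change.** In section 2.4 (Safety) and section 2.9, add the following beside the adverse-event review, from the C-SSRS at baseline, post-intervention and 6 months:

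1. A shift table of ideation severity against the recent (not lifetime) baseline rating, with n/N and exact 95% CI for participants at a higher level at each time point. Include a row for no ideation, since the described scale starts at 1, and state how many were not assessed.
2. n/N with any new suicidal behaviour since baseline. Show non-suicidal self-injury separately, because the behaviour scale includes it and participants enter with self-harm.
3. Individual trajectories for all 20 participants, adding FIT-session scores where they are in the research data. The protocol places baseline and outcome measures in Qualtrics but does not say this of session scores.

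Use counts in place of mean and Cohen's d for the behaviour component. Keep average ideation change as the secondary effectiveness summary. State the recall period at each contact, since the C-SSRS version is named only for screening. If an any-contact, worst-value count is also shown, say that repeated measurement biases it upward and that phone sessions do not use the C-SSRS.

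The sponsor should reconcile sections 2.7 and 3.3 on how C-SSRS findings relate to adverse-event recording. No clinical threshold is proposed here.

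**Cost.** One paragraph, one table and one listing, with no change to sample size or assessments. The safety summary may look less favourable. Without a control group it cannot separate a treatment effect from natural fluctuation, and the report should say so.
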